In summary, this study will use the PROMIS Upper Extremity Score for Children at 1 year after randomisation as the primary outcome measure. The total number of patients required to obtain a power of 90% to detect a 4-point difference between groups for the primary outcome measure will be 266; i.e. 133 patients will be required in each treatment group. With an allowance for a conservative 20% loss to follow-up, we plan to recruit 334 patients in total. To maximise trial efficiency, we will re-estimate the sample size based on the SD of the outcome tool at 6-months follow-up of the first fifty children in the trial.

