3.2 Randomisation and Blinding

Patients will be randomised after consent. All hospital treatment areas have access to the internet so will access the randomisation service in real time i.e. there will be no delay in patient treatment.

Consenting participants will be allocated randomly (1:1) to either operative fixation or non-surgical treatment. Randomisation will be performed using a minimisation algorithm to ensure balanced allocation of participants across the two treatment groups, stratified by centre and dislocation status of the elbow at presentation in the emergency department (i.e. dislocated or not dislocated). The first 30 participants will be randomised using a simple randomisation schedule produced by the trial statistician, to seed the minimisation algorithm, and a non-deterministic probabilistic element will be introduced to prevent predictability of the treatment allocation.

Stratification by centre within the minimisation algorithm will help to ensure balanced treatment assignment within centre so that any unobserved factors (e.g. case-mix) contributing to between-centre variation in practices are balanced between treatment arms. The catchment area (the local population served by the hospital) will be similar for all hospitals; each hospital being a children's injury unit dealing with these fractures on a regular basis. All of the recruiting hospitals, and indeed all hospitals throughout the NHS, use these techniques as part of their normal practice i.e. staff will already be equally familiar with both forms of treatment. This cannot eliminate the clinician-specific effect of an individual at any one centre. However, since the procedures are commonplace across the NHS, many clinicians will be involved in the management of this group of patients; likely between 5 and 20 clinicians at each centre, including consultants and trainee surgeons. Therefore, we anticipate that each individual clinician will only treat a handful of those enrolled in the trial, reducing the risk of a clinician-specific effect upon the outcome in any one centre.

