3.3 Sample Size

Extremity Score for Children. Raw scores are translated into standardised T scores with a population mean of 50 and a Standard Deviation (SD) of 10. The 'Minimally Clinically Important Difference' (MCID) for the PROMIS Upper Extremity Score amongst children with milder forms of disability has been demonstrated to be three to

four [11], we seek to find a difference of four points. Assuming a SD of 10, a total of 266 patients (133 in each arm) is required to provide 90% power at the 5% level (two-sided) to detect a 4-point difference between the groups. Allowing for a conservative 20% loss to follow-up, we plan to recruit 334 patients in total for this trial (167 per arm).

The SD of 10 derived by PROMIS was based on a sample of children with a higher proportion of chronic illness than the general population [12], and it is anticipated that the variation in outcomes in the treatment of acute medial epicondyle fractures is likely to be less than in a chronic illness.

Independent verification of the sample size is available in

Z:\CSM_SCIENCE\Statistical Analysis\4. Sample Size**SCIENCE_SampleSize_Verification_04Apr2019.docx**, stored in the confidential statistical section of the TMF.

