3.6 Blinded analysis

A blinded analysis of the data (not separated by treatment arm) will be undertaken prior to the final data lock to undertake data cleaning, to look into the distribution of variables, missing data distributions, and to review exclusions associated with the per protocol population.

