Model Checking and normalising transformations: Assumptions of normality will be assessed graphically looking at residual and quantile-quantile (QQ) plots, and data transformation will be considered if model assumptions (particularly normality of residuals) are clearly violated. Mixed-effects models are robust to small deviations from normality in the residuals; however, if approximate normality cannot be achieved the data normalising transformations will be considered and then proceed fitted the same mixed effects linear model described above on the transformed scale. We will use the logistic transformation which is a transformation recommended for bounded outcomes [32]. Data will be first transformed to a (0, 1) scale (transformed y_new=(γ -min(γ))/(max(γ)-min(γ)), where γ represents the outcome), following Smithson et al [33] and using the logistic transformation, in line with the bounded nature of the measurement scale. Treatment effect estimates will be presented on the original scale by post-estimation back transforming.

Examination of residuals following model fitting will be undertaken including exploration of dependencies with observed covariates. Consideration will be given to augmenting the model to heteroscedastic (level 1) residuals especially when the model is fitted in the original scale, where strong patterns are observed between residual errors and covariates and variance increases with the mean [34]. It is expected that normalising transformation using the logistic transform will have a variance stabilising effect on the fitted model and

maybe preferable as it would result to a simplified model. Comparison of the log-likelihood values of a small number of competing models will be used to decide whether model (higher log-likelihood values indicate a better fitting model).

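### SAP 6.2 appears to let raw log-likelihoods choose between the T-score and logit versions of the primary model, and these are not comparable across scales

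*SAP*

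**What the plan says.** The relevant text is the part of SAP 6.2 on model checking and normalising transformations. It runs in this order.

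1. Residual and quantile-quantile plots are inspected. A transformation is considered only when the assumptions clearly fail, and mixed models are said to tolerate small departures.
2. If needed, the score is rescaled to the unit interval, put through the logit, and the same mixed model is fitted. Treatment effects are then back-transformed to the original scale.
3. On the original scale, residual variances that differ with covariates or with the mean may be modelled instead. The logit version is expected to stabilise the variance and is described as "maybe preferable as it would result to a simplified model".
4. The closing sentence reads "Comparison of the log-likelihood values of a small number of competing models will be used to decide". What is to be decided is not stated, because the sentence breaks off. A bracket adds that a higher log-likelihood means a better fit.

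The SAP gives no Jacobian term, common scale, information criterion or restriction to models of one outcome. Separately, SAP 3.6 states: "A blinded analysis of the data (not separated by treatment arm) will be undertaken prior to the final data lock". Its purposes include looking at the distributions of variables.

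**The concern.** Step 4 follows directly on a contrast between an original-scale model and a logit model, so the natural reading is that log-likelihood arbitrates between them. A log-likelihood for the T-score is measured per T-score point and one for the logit is measured per logit. Changing the unit changes the value even when the data and the fit are identical.

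The scale of the primary model is at stake. The estimand in SAP Table 1 is a mean difference on the PROMIS scale, and the sample size is set in T-score points. A test carried out on logits is a different test, even if the estimate is later expressed in points. An invalid rule could therefore settle which primary p-value and interval are reported, for a reason unrelated to fit.

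**Working it through.** **The plan's own figure.** The disputed text contains no number, but the sample size fixes the scale and spread to use. SAP 3.3 says "we seek to find a difference of four points" and "Assuming a SD of 10, a total of 266 patients (133 in each arm) is required", for "90% power at the 5% level (two-sided) to detect a 4-point difference between the groups". By the normal approximation, n per arm = 2 × (1.960 + 1.282)² × 10² / 4² = 131.3, so 132 (264 in total). The plan's 133 per arm gives 90.4% power. Allowing for 20% loss, 133 / 0.8 = 166.25, so 167 per arm and 334 in total. The plan's figures reproduce.

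**Inputs.** Bounds 10 to 58, width 48 (SAP 6.1). Five occasions including baseline (SAP 6.2), so at most 334 × 5 = 1,670 observations.

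**Effect of units alone.** Dividing the T-score by 48 changes nothing about the fit but adds ln 48 = 3.871 per observation, or 1,670 × 3.871 = 6,465. In one simulated data set the log-likelihood moved from -4,990 to +1,475.

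**The missing term.** With z = logit((y - 10)/48), dz/dy = 48 / ((y - 10)(58 - y)). The logit model's log-likelihood for the T-score is its raw value plus the sum of ln(dz/dy). At y = 34 this is ln(48/576) = -2.485 per observation. At y = 50 it is ln(48/320) = -1.897. At y = 57.5 it is ln(48/23.75) = +0.704. Omitting it flatters the logit over most of the range and penalises it only very near the bound.

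**Simulation.** Maximum-likelihood mixed models (visit by treatment, random participant intercept) were fitted to 10 data sets per setting. Means, spreads and ceiling rates are assumptions. So is a small adjustment that moves scores off exact 0 and 1. Centre effects and random slopes were left out. Values are averages.

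| Simulated scores | At ceiling | SD, T / logit | T-score | Logit, raw | Logit + Jacobian | Raw rule picks logit | Corrected rule picks logit |
|---|---|---|---|---|---|---|---|
| Normal on T-score | 0% | 6.33 / 0.59 | -4978 | -1025 | -5041 | 10/10 | 0/10 |
| Mid-scale recovery | 1% | 10.02 / 1.39 | -5332 | -2429 | -6028 | 10/10 | 0/10 |
| High recovery | 11% | 10.66 / 2.57 | -5220 | -3459 | -5568 | 10/10 | 0/10 |
| Strong ceiling | 34% | 11.70 / 3.59 | -5219 | -3669 | -3252 | 10/10 | 10/10 |
| Normal on logit | 0% | 12.68 / 1.46 | -5908 | -2288 | -5616 | 10/10 | 10/10 |
| Mean 56 throughout | 8% | 1.32 / 1.51 | -2560 | -2869 | -3164 | 0/10 | 0/10 |
| Mean 57 throughout | 12% | 0.76 / 1.56 | -1652 | -2916 | -1968 | 0/10 | 0/10 |

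A separate run of 50 data sets agreed. With normal T-scores the logit was chosen in 50 of 50 raw and 0 of 50 corrected. With scores packed near the bound the raw rule chose the T-score in 50 of 50.

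**Reading the table.** The raw rule picks whichever outcome has the smaller residual SD in its own units. With 1,670 observations and the adjustment used, logits lie within ±ln(3,339) = ±8.1, so their SD cannot exceed 8.1. At the plan's SD of 10, taken as a marginal SD, the logit is therefore favoured. In the first three settings the T-score model fits better and the raw rule still rejects it. In the other four the raw and corrected rules agree.

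**The case against.** The strongest reply has several parts.

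- **The plots come first.** A reader might infer that likelihood alone picks the scale. The documents do not support that: the logit is considered only after a clear graphical failure. Scores exactly normal on the T-score should not reach the likelihood step, so 10 of 10 is not the plan's error rate. This stands. However, the graphical check has no numerical threshold, and the rule also misleads in the 11% ceiling setting, where a departure from normality could well be seen.
- **The sentence names no models.** It could mean only residual structures on one scale, where the likelihoods are comparable. This cannot be excluded. Even then, raw log-likelihood cannot fall when a nested model is enlarged, so a penalty or test is needed. A reader might infer that the more complex model is always kept. That goes too far, because the SAP considers unequal variances only where strong patterns appear and it values simplicity.
- **The logit does not always win.** A claim that it is chosen whatever the data look like is false, as the last two rows show. Such data are implausible here, because scores taken before randomisation, soon after the fracture, are in the model.
- **Estimates are back-transformed.** The result would not be reported in logits. This stands for presentation, but the model and test would still be on the logit scale.
- **Timing.** A reader might infer that the choice is made after unblinding, because it follows the fitting of a model with treatment terms. The SAP does not say when it is made, so this is only an inference.

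**Conclusion.** The point holds in conditional form. If SAP 6.2 uses raw log-likelihoods to choose between the T-score and logit models, as its context most naturally suggests, the comparison is invalid. Once both are fitted it almost always favours the logit at plausible spreads, in the simulated settings by about 1,550 to 3,950 units (for example -3669 against -5219, and -1025 against -4978). It did so in three settings where the T-score model fitted better by 63 to 696 units after correction (-4978 against -5041, and -5332 against -6028). Scores packed near the upper bound reverse the preference.

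This rests on the reading of an incomplete sentence, on assumed score distributions and on an assumed handling of scores at the bounds. The handling of the bounds weighs most on the settings with many scores at the ceiling. I give no figure for the effect on the primary p-value, because that also depends on it. The logit option itself is a reasonable prespecified remedy for a bounded score; the defect lies in the rule for choosing it.

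**What to change.** Amend SAP 6.2 as follows.

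- Complete the sentence: name the models compared and the decision to be made.
- Limit likelihood comparisons to models of the same outcome on the same observations, fitted by ML rather than REML, and judge them by AIC or a likelihood-ratio test.
- If scales are compared, add the Jacobian sum to the logit model's log-likelihood.
- Write out how scores at the bounds are moved off 0 and 1. The printed rescaling formula gives exactly 0 and 1 at the extremes, where the logit is infinite. Dropping those rows would leave the two models fitted to different observations.
- Preferably settle the scale in the SAP 3.6 blinded review, on pooled data without treatment terms, and freeze it before lock.
- State how this route relates to Protocol 10.1, which plans unadjusted non-parametric tests if the outcome is not normal.

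The cost is wording and slightly more analysis work; no new data are needed. Fixing the T-score scale outright would also remove the problem, but it gives up a prespecified remedy for a bounded outcome and is a matter of judgement.

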6.3 Outcome measures

To ensure the correct outcome domains are being collected, we have undertaken an exercise to ratify the outcomes collected in this trial. A systematic review identified 52 outcome domains that have been previously used to record success/failure in medial epicondyle fractures. A Delphi process considered the views of 25 physiotherapists, 39 UK children's orthopaedic surgeons, 17 surgeons from international orthopaedic trials groups, 20 parents of affected children and 10 affected children. The most important outcome domains are now apparent in the final stages of formalising the Core Outcome Set.

Core Outcomes apparent from Delphi exercise:

• Activities of Daily Living (ability to dress/wash/eat).

20JUN2024 | V7.0

- Participation in School Activities
- Ability to resume participation in hobbies and sports.
- Pain
- Complications (Nerve Injury, infection, metalwork prominence, review of any available routinely collected digital images of the elbow stored in the PACS archive).

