5.3 Baseline Characteristics

Baseline comparability of the randomised groups on stratification factors will be presented (Table 5). Baseline comparability of the randomised groups on other important prognostic factors and values of primary and secondary outcomes will be considered by treatment allocation. One of the stratification factors includes sites. A large number of sites is participating and a number of them has recruited a small number of participants. Sites with a small number of participants (<5) will be grouped together and marked as such when presenting baseline counts by site as this is how they will be handled in the analyses (Section 6.2.).

Variables will be presented by intervention arm numbers (with percentages) for binary and categorical variables and means and standard deviations (SDs), or medians and interquartile ranges (IQRs) for continuous variables will be presented; there will be no tests of statistical significance nor confidence intervals for differences between randomised groups on any baseline variable (Table 6-7).

Outcomes reported only for subgroup of participants will be clearly marked and footnotes explaining the nature of selective response e.g. DASH S/PA module is administered only to those participating at sports. Separate comparative Table presenting the descriptive statistics for the remaining of the outcomes at baseline for each subgroup with and without a measurement e.g. An additional baseline table of all outcomes measured for all for the group participating at sport and the group which does not.

Table 5: Stratification factors used in minimisation algorithm, by treatment allocation

| Stratification Factor | - | Operative fixation | | Non-operative treatment | | otal |
|---|---|--------------------|---|----------------------------|---|------|
| | n | % | n | % | n | % |
| Centre | | | | | | |
| Alder Hey Children's Hospital | | | | | | |
| Bradford Royal Infirmary | | | | | | |
| Bristol Royal Hospital for Children | | | | | | |
| Countess of Chester Hospital | | | | | | |
| Derriford hospital | | | | | | |
| Hull Royal Infirmary | | | | | | |
| James Cook University Hospital (Middlesbrough) | | | | | | |
| Jenny Lind Children's Hospital (Norwich) | | | | | | |
| Leeds general Infirmary | | | | | | |
| Leicester Royal Infirmary | | | | | | |
| Medway Maritime Hospital | | | | | | |
| Nottingham University Hospital (Queen's Medical Centre) | | | | | | |
| Royal Berkshire Hospital | | | | | | |

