Outcomes measured in certain subgroups only: The secondary outcome DASH Sports/Performing arts module is only completed if the participant indicates regular participation in sport or musical activities. The analysis of this secondary outcome, **targeting the average treatment effect in the subgroup completing the DASH Sports/Performing arts module**, will use the same methods described for the primary outcome but augmented with propensity score weighting. As this subgroup is exclusively observed among participants engaged in sports and musical activities, this could probably lead to imbalances in covariates between the comparison groups. The propensity weighting scheme is selected because it maximises the efficiency of the estimate and provides an unbiased estimate of the subgroup average treatment effect due to randomisation. [35, 36]. The inverse probability treatment weighting (IPTW) scheme for the propensity of receiving the randomised treatment will be modelled as a function of baseline covariates including subgroup membership, age, sex, stratification factors, initial dislocation status, mechanism of injury, baseline pain score. All interactions between group membership and the rest of the baseline covariates will be included in this adjustment set [37].

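### The SAP calls the weighted DASH Sports/Performing Arts effect unbiased by randomisation, but never says when the participation that defines the analysed subgroup is judged

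*SAP*

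**What the plan says.** SAP 6.2, under outcomes measured in certain subgroups only, states that the module "is only completed if the participant indicates regular participation in sport or musical activities". It describes the analysis as "targeting the average treatment effect in the subgroup completing the DASH Sports/Performing arts module", using the repeated-measures methods of the primary outcome plus inverse probability weighting. It expects that restricting to this subgroup "this could probably lead to imbalances in covariates between the comparison groups", and says the weighting "provides an unbiased estimate of the subgroup average treatment effect due to randomisation". The propensity of receiving the randomised treatment is "modelled as a function of baseline covariates including subgroup membership, age, sex, stratification factors, initial dislocation status, mechanism of injury, baseline pain score", with interactions between membership and the other covariates.

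SAP 5.3 words the filter more narrowly: "DASH S/PA module is administered only to those participating at sports". It also plans a baseline table of the other outcomes "for the group participating at sport and the group which does not".

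The module is scheduled before randomisation and at 6 weeks, 3, 6 and 12 months (Protocol Table 1; SAP 6.1 adds 4 weeks). Protocol 6.3 lists "Ability to resume participation in hobbies and sports" among the core outcomes, and secondary objective 2 (Protocol 6.2.2) concerns participation in sport and performing arts. SAP section 7 names DASH S/PA a key secondary outcome.

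**The concern.** Randomisation makes the arms comparable within a subgroup whose membership is settled before allocation, or cannot be changed by treatment. The SAP asserts the resulting unbiasedness without saying that membership meets either condition. Its target set is defined by completing the module, and the module is offered repeatedly up to 12 months.

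Treatment could plausibly affect participation. Protocol section 5 cites expectations of early mobilisation and return to sport as a driver of surgery, and Protocol 5.2 leaves open whether bony union matters for return to sport. If a child who is not playing at 12 months gives no 12-month score, the arm that returns more children to sport also brings in more children with weaker recovery. The module comparison is then tilted against that arm. No comparison of participation by arm is planned that would show this happening.

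**Working it through.** **1. When is membership set?** No sentence in either document dates the participation question.

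- Pointing to baseline: SAP 6.2 lists membership among the baseline covariates, and SAP 5.3 plans a baseline table by sport participation.
- Pointing to follow-up: the target is the group completing a module that is offered at every visit, and completion depends on indicating participation.

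Two analysts could build different analysis sets from this text, one protected by randomisation and one not.

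**2. Size before weighting, if membership is set at follow-up.** Assume a normal latent tendency to take part that has correlation ρ with the module score (SD 1, higher = better), participation p1 and p0 in the two arms, and no true effect. With z the standard normal quantile of p,

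bias = ρ × [φ(z1)/p1 − φ(z0)/p0].

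The term φ(z)/p is 0.350 at 80%, 0.497 at 70% and 0.798 at 50%. For ρ of 0.5 to 0.7:

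- 80% v 70%: 0.350 − 0.497 = −0.147, giving −0.07 to −0.10 SD.
- 70% v 50%: 0.497 − 0.798 = −0.301, giving −0.15 to −0.21 SD.

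These figures ignore the planned weighting, so they are not the bias of the planned estimator.

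**3. Size after weighting.** This was simulated with 400,000 children per setting and no true effect. Score and participation each depend on one measured baseline covariate (loading 0.3 on both) and on unmeasured recovery (loading λ on both). Participation also depends on arm. The analysis is inverse probability weighting on the measured covariate, then weighted regression among participants. Bias in SD:

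| Participation by arm | λ = 0.3 | λ = 0.5 | λ = 0.7 |
|---|---|---|---|
| 70% v 70% | −0.003 | 0.002 | 0.001 |
| 65% v 75% | −0.018 | −0.036 | −0.076 |
| 60% v 80% | −0.022 | −0.082 | −0.152 |
| 50% v 80% | −0.047 | −0.119 | −0.230 |

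With membership fixed at baseline (λ = 0.5) the bias is −0.001, zero within simulation error.

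At 60% v 80% and λ = 0.5, the unweighted bias is −0.106 and weighting brings it only to −0.082. Weighting removes the part carried by the measured covariate and leaves the part carried by unmeasured recovery.

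**4. Against the precision available.** The SAP gives no figure for this subgroup, so the primary outcome's 133 followed up per arm is used (SAP 3.3). At 60% v 80% that leaves 133 × 0.60 = 79.8 and 133 × 0.80 = 106.4 children, and SE = √(1/79.8 + 1/106.4) = 0.148 SD. Rejection rates at the two-sided 5% level with no true effect, 4,000 replicates each:

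- Membership fixed at baseline, λ = 0.5: 5.9%.
- λ = 0.5: 6.0% at 65% v 75%, 8.6% at 60% v 80%, 13.5% at 50% v 80%.
- λ = 0.7: 21.4% at 60% v 80%, 39.2% at 50% v 80%.

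**5. The plan's own sample size.** It reproduces. A t-test with a 4-point difference and SD 10 has 90.1% power at 133 per arm, and 133/0.8 = 166.25, rounded up to 167 per arm, or 334. Nothing here changes it.

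**The case against.** A reader might infer that the question is re-asked at each visit, so that the DASH analysis is certain to compare differently selected children. The documents do not support that. Membership is listed as a baseline covariate. The module is also given before randomisation, to children whose fracture is at most two weeks old, so regular participation may well mean the child's usual habit. On that reading the unbiasedness wording is defensible and the imbalances the SAP expects are chance ones.

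A reader might also infer that children who have not resumed sport drop out of the analysis altogether. That too goes beyond the text. The primary outcome's mixed model uses all available visits, so a child with a baseline or earlier module score still contributes under missing at random. That assumption is doubtful when the score is absent because the child is not playing. The sensitivity analyses in SAP Table 1, 6.3 and 6.4 that relax it are written for PROMIS.

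Nor do the figures show that the result would point the wrong way. At 65% v 75% the bias is at most about half a standard error, and at λ = 0.5 the rejection rate matches the baseline-defined reference. Material distortion needs participation gaps of 20 to 30 points.

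What this leaves standing is the ambiguity. Calling membership a baseline covariate does not say who answers at 12 months. Read literally, the completion rule lets a baseline participant who has stopped playing give no score.

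**Conclusion.** The point holds as a conditional one. The SAP makes an unbiasedness claim that depends on when participation is judged, and does not settle that timing. With membership fixed before randomisation and the module asked of those children throughout, the claim is right. With membership set at follow-up it is not justified, and weighting on baseline covariates does not restore it. The bias left after weighting is then about 0.02 to 0.08 SD at 65% v 75% participation and 0.02 to 0.15 SD at 60% v 80%, and zero in this model if participation is equal.

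The participation rates, the loadings and the single measured covariate are all assumptions, and the documents give none of them. The matter is confined to one key secondary outcome and should be corrected before analysis.

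**What to change.** 1. Define the DASH S/PA analysis set by the participation answer given before randomisation, and analyse it as randomised. State whether those children are asked the module at every visit, and align the sport-only wording of SAP 5.3 with the sport-or-music wording of SAP 6.2.
2. Report participation (yes/no) by arm at each visit where it was recorded, with a risk difference and 95% confidence interval. This also serves secondary objective 2.
3. Add a sensitivity analysis over a range of values for baseline participants without a follow-up module score. A baseline-defined set does not by itself repair scores that are missing because the child was not taking part. A rule giving the worst score to children kept out of sport by the elbow cannot be presumed feasible, because the documents do not show that the reason for not resuming is collected.
4. Describe the weighting as covariate adjustment, and limit the unbiasedness statement to the baseline-defined set.

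The cost is SAP wording, one binary summary and one further sensitivity analysis.
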